9.6 DATA MANAGEMENT

The data from enrolled patients in this study will be recorded on a CRF or other applicable forms. The designated CRO will capture, check, store and analyze the data. The designated CRO will follow Boehringer Ingelheim standard operating procedures (SOPs) and their own internal SOPs.

A data management plan (DMP) will be created to describe all functions, processes, and specifications for data collection, cleaning, and validation.

Data will be transferred to Boehringer Ingelheim after the closure of the study.

9.7 DATA ANALYSIS

Analyses will be performed by a designated CRO. The main analysis population will consist of all eligible patients (i.e. all patients who have signed the informed consent and fulfilled all inclusion criteria and no exclusion criteria). In addition, all eligible patients will be categorized into Cohort A (patients switched from VKA to Pradaxa®) and Cohort B (patients newly initiated Pradaxa® or VKA). Cohort B will be further classified into 2 groups, the Pradaxa® initiators or the VKA initiators. The 2 cohorts and the 2 subgroups will be used in corresponding PACT-Q analyses.

Analytic specifications, including tables and listings, will be detailed in the statistical analysis plan (SAP) that is separate from the full study protocol.

Statistical analysis of all data will be performed using the latest version of SAS® statistical software (SAS Institute, Cary, NC, USA). All statistical tests are two sided and statistical significance level of 0.05 will be used.

9.7.1 Main analysis

Baseline demographic and clinical characteristics

Descriptive summary will be presented for baseline demographic and clinical characteristics of all patients enrolled in Cohort A, Cohort B Pradaxa® initiators, and Cohort B VKA initiators, respectively. For continuous variables, number of patients, mean, standard deviation (SD), median, Q1 (lower quartile), Q3 (upper quartile), minimum, and maximum will be presented. For categorical variables, frequency and percentage will be presented for each category.

Primary outcomes

For Cohort A, descriptive summary will be presented for PACT-Q2 score at baseline visit (Visit 1), Visit 2, and Visit 3 using measure of central tendency and variation (mean \pm SD, or median with inter-quartile range (IQR)). The PACT-Q2 score at Visit 2 and Visit 3 will be compared with the PACT-Q2 score at baseline visit, respectively, using paired t-test or Wilcoxon signed-rank test based on the distribution of the data.

For Cohort B, the patients newly initiated Pradaxa® or VKA will be matched with a ratio of 1:1 based on the propensity score. The covariates age, gender, body weight, CHA₂DS₂-VASC score, HAS-BLED score, kidney function (creatinine clearance), stroke and/or bleeding related risk factors, co-morbidities, and/or concomitant therapies, **if available**, will be included in the propensity score model. Details of the propensity score model and the matching procedure, such as the choice of algorithm and caliper width will be specified in the SAP. Descriptive summary of the baseline characteristics will be presented for and compared between the matched patients to check the balance of baseline characteristics between the two groups of Cohort B after propensity score matching. Moreover, standardized difference will be calculated as a measure of the balance of baseline characteristics after propensity score matching. Analyses of PACT-Q2 score will be performed on propensity score matched Pradaxa® initiators and VKA initiators. Descriptive summary will be presented for PACT-Q2 score at Visit 2 and Visit 3 using mean \pm SD, or median with IQR. PACT-Q2 score will be compared between matched Pradaxa® initiators and VKA initiators using paired t-test or Wilcoxon signed-rank test.

Secondary outcomes

For Cohort A, the PACT-Q2 score at Visit 2 and Visit 3 will be compared using paired t-test or Wilcoxon signed-rank test based on the distribution of the data.

For Cohort B, descriptive summary will be presented for PACT-Q1score at baseline visit using mean \pm standard deviation, or median with IQR, and will be performed on all patients in Cohort B and by treatment (Pradaxa® or VKA).

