	
Characterization of patients from both cohorts according to:
 
Demographics: Age, gender, race, education level, height, weight, and BMICo-morbiditiesConcomitant therapiesStroke- and/or bleeding related risk factors in the medical historyCHA₂DS₂-VASc scoreHAS-BLED scoreKidney function (creatinine clearance)Dosing of Pradaxa® and the reasons for dose changeDuration of previous VKA treatment (for Cohort A only)									
Data sources:	Source data are collected from medical charts and the questionnaires (PACT-Q) completed by the enrolled subjects at approximately 20 medical centers or regional hospitals. A case report form will be designed for data collection.									
Study size:	
It is planned that approximately total 1000 patients from around 20 medical centers or regional hospitals will be recruited in the study. An estimated sub-group allocation basing on real-world practice in Taiwan includes approximately 300 patients in Cohort A (patients switched from VKA to Pradaxa®) and around 700 patients in Cohort B (patients newly initiated Pradaxa® or VKA), with about 500 patients receiving Pradaxa® and 200 patients receiving VKA. Consecutive enrolment will be performed to minimize selection bias. The actual number of patients in each cohort will be according to the patient distribution in the real-world practice.
 

Total number	1000	

Estimated number in sub-grouping	Cohort A—VKA switches to Pradaxa®	300	

Cohort B—Newly initiator	Pradaxa® VKA	500 200	

	Total number		1000	Estimated number in sub-grouping	Cohort A —VKA switches to Pradaxa®	300	Cohort B —Newly initiator	Pradaxa® VKA	500 200
Total number		1000								
Estimated number in sub-grouping	Cohort A —VKA switches to Pradaxa®	300								
	Cohort B —Newly initiator	Pradaxa® VKA	500 200							

Data analysis:	
A Data Management Plan (DMP) and Statistical Analysis Plan (SAP) will be prepared to describe all processes, variables, and specifications for data collection, cleaning, validation, and analyses.

	
The study is essentially descriptive. All patients who have signed the informed consent and fulfilled study criteria will be included in the main analysis.

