8. RESEARCH QUESTION AND OBJECTIVES

Objective 1

To describe the treatment perception from patients with non-valvular atrial fibrillation (NVAF) receiving Pradaxa® or VKA for stroke prevention by using the self-estimation questionnaire of PACT-Q during a 6-month study period.

Objective 2

To investigate the patient's characteristics.

Two cohorts of patients will be recruited:

Cohort A:

Patients who had been treated with VKA and have switched to Pradaxa®.

Cohort B:

Patients who are newly diagnosed with NVAF and initiated on either Pradaxa® or VKA.

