9.5 STUDY SIZE

It is planned that approximately 1000 patients from around 20 medical centers or regional hospitals will be recruited in the study. An estimated sub-group allocation basing on real-world practice in Taiwan includes approximately 300 patients in Cohort A (patients switched from VKA to Pradaxa[®]) and around 700 patients in Cohort B (patients newly initiated Pradaxa[®] or VKA), with about 500 patients receiving Pradaxa[®] and 200 patients receiving VKA. Consecutive enrolment will be performed during whole recruitment period to minimize selection bias. The actual number of patients in each cohort will be according to the patient distribution in the real-world practice.

Total number		1000
Estimated number in sub-grouping	Cohort A —VKA switches to Pradaxa®	300
	Cohort B —Newly initiator	Pradaxa® 500 VKA 200

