## 7.4 Sample Size

It is planned that approximately 1000 patients from around 20 medical centers or regional hospitals will be recruited in the study. An estimated sub-group allocation basing on real-world practice in Taiwan includes approximately 300 patients in Cohort A (patients switched from VKA to Pradaxa®) and around 700 patients in Cohort B (patients newly initiated Pradaxa® or VKA), with about 500 patients receiving Pradaxa® and 200 patients receiving VKA. Consecutive enrolment will be performed during whole recruitment period to minimize selection bias. The actual number of patients in each cohort will be according to the patient distribution in the real-world practice.

Total number		1000	
Estimated number in sub-grouping	Cohort A —VKA switches to Pradaxa®		300
	Cohort B —Newly initiator	Pradaxa®	500
		VKA	200

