### 11.3 Primary Endpoint Analysis

Mean values and mean change from baseline of PACT-Q2 scores will be presented as descriptive statistics including Number, Mean $\pm$ SD, Median, Range, inter-quartile range (IQR), 25th percentile, 75th percentile and 95% C.I. The changes under Cohort A will be calculated as (PACT-Q2 scores at Visit 2 minus PACT-Q2 scores at visit 1, PACT-Q2 scores at Last Visit minus PACT-Q2 scores at visit 1). The difference under cohort B will be calculated as (PACT-Q2 scores of Pradaxa® minus PACT-Q2 scores of VKA at Visit 2, PACT-Q2 scores of Pradaxa® minus PACT-Q2 scores of VKA at Last Visit). Shapiro-Wilk test will be conducted for testing the normality. If the null hypothesis of normally distributed of Shapiro-Wilk test is not reject, two-sided paired t-test will be performed and obtain the p-value. Significant level of the test will be set as 0.05. Once significant result of Shapiro-Wilk test is lower than 0.05, Wilcoxon signed rank test will be used instead.

For cohort B, the patients newly initiated Pradaxa® or VKA will be matched with a ratio of 1:1 based on the propensity score with caliper matching. After the propensity score each patient is generated, both Pradaxa® group and VKA group should be randomly sorted and then the first VKA unit is selected to find its closest

Pradaxa® match in terms of the propensity score. The random seed will be set as 20190218. The caliper will be set as 0.001.

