### Cohort B (patients newly initiated Pradaxa® or VKA)

- Description of mean PACT-Q1 score at baseline. Mean values of PACT-Q2 scores will be presented as descriptive statistics including Number, Mean  $\pm$  SD, Median, Range, inter-quartile range (IQR), 25th percentile, 75th percentile and 95% C.I.

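### Cohort B PACT-Q2 appears to be summarised only in 1:1 matched pairs, which at the planned split would leave at least 300 of 500 Pradaxa initiators without a PACT-Q2 result at Visits 2 and 3

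*Protocol*

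**What the plan says.** Protocol section 8 gives Objective 1 as "To describe the treatment perception from patients with non-valvular atrial fibrillation (NVAF) receiving Pradaxa® or VKA for stroke prevention", using the PACT-Q over six months. The protocol abstract calls the study essentially descriptive and adds: "All patients who have signed the informed consent and fulfilled study criteria will be included in the main analysis". Protocol 9.7 likewise takes all eligible patients as the main analysis population, and says the two cohorts and the two Cohort B subgroups serve the corresponding PACT-Q analyses. SAP section 9 puts efficacy on the FAS, which SAP 8.3 defines as all eligible patients.

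For the Cohort B primary outcome, protocol 9.7.1 is narrower. It states that "the patients newly initiated Pradaxa® or VKA will be matched with a ratio of 1:1 based on the propensity score" and, after the balance checks, that "Analyses of PACT-Q2 score will be performed on propensity score matched Pradaxa® initiators and VKA initiators". The next sentence promises summaries at Visits 2 and 3 without naming a patient set, and the one after it gives the paired test in matched patients. The abstract repeats the matched restriction.

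SAP 11.3 promises PACT-Q2 means, defines the Cohort B quantity as the Pradaxa-minus-VKA difference at each visit, and then describes the matching: patients are randomly sorted, "the first VKA unit is selected to find its closest" Pradaxa counterpart, and the caliper is 0.001. SAP 11.4, under the Cohort B PACT-Q1 endpoint, also says "Mean values of PACT-Q2 scores will be presented as descriptive statistics", with no visit, treatment split or population.

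**The concern.** Matching serves the comparison of the two treatments. It does not serve a description of either group. A 1:1 match started from the smaller group keeps at most one Pradaxa patient for each VKA patient, chosen because the two resemble each other. A mean and SD from that subset describe the Pradaxa initiators who overlap with VKA users, and these need not match the figures for Pradaxa initiators in practice. Pradaxa initiators are the largest planned group in the study.

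Where the authors meant a wider set, they said so. In protocol 9.7.1 the baseline summaries cover everyone enrolled in each group, and PACT-Q1 is summarised in all of Cohort B and by treatment. PACT-Q2, the primary outcome, has no such wording. If the programmer follows protocol 9.7.1 as written, the descriptive objective is answered for Cohort B only in the matched subset.

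**Working it through.** **Inputs**
- Planned sizes (protocol 9.5, SAP 7.4): Cohort A 300; Cohort B "with about 500 patients receiving Pradaxa® and 200 patients receiving VKA".
- Matching: 1:1 (protocol 9.7.1), started from each VKA patient, caliper 0.001 (SAP 11.3).
- No imputation (SAP 8.5).

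**Planned total.** 300 + 500 + 200 = 1000, and 500 + 200 = 700 for Cohort B. Both agree with the documents. The plan gives no effect size, SD or power, so there is no sample-size formula to reproduce.

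**Bound at the planned split**
- Maximum pairs = min(500, 200) = 200.
- Pradaxa initiators outside the matched set: at least 500 − 200 = 300.
- As shares: 300/500 = 60% of Pradaxa initiators, 300/700 = 43% of Cohort B, 300/1000 = 30% of the study.

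The SAP does not say whether a Pradaxa patient may be used twice. The bound holds either way: 200 VKA patients with one match each cannot draw in more than 200 distinct Pradaxa patients.

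**Sensitivity to the split.** The sizes are estimates: "The actual number of patients in each cohort will be according to the patient distribution in the real-world practice".

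| Pradaxa : VKA | Minimum unmatched Pradaxa |
|---|---|
| 550 : 150 | 400 |
| 500 : 200 | 300 |
| 450 : 250 | 200 |
| 350 : 350 | 0 |

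**Effect of the caliper.** A caliper can only remove pairs. To show by how much, greedy nearest-neighbour matching without re-use was simulated (200 runs per row), with the 0.001 caliper applied to the propensity score itself. The separation between groups is an assumption, because the documents give none. In the zero row the estimated scores vary by noise alone, with an SD of 0.3 on the logit scale.

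| Assumed separation (SD) | Mean pairs | Unmatched Pradaxa (of 500) | Unmatched VKA (of 200) |
|---|---|---|---|
| 0 | 178 | 322 | 22 |
| 0.5 | 152 | 348 | 48 |
| 1.0 | 105 | 395 | 95 |
| 1.5 | 68 | 432 | 132 |

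So some VKA initiators would drop out as well.

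**Does the SAP supply the missing summary?** SAP 11.3 speaks of means and of change from baseline, but Cohort B completes no PACT-Q2 at baseline (protocol 9.2.3 and 9.3.5), so the change cannot apply there. What it defines for Cohort B is the between-treatment difference, followed by the matching rule. The sentence in SAP 11.4 may be a slip for PACT-Q1. Neither section sets out a table by treatment in all eligible Cohort B patients, and SAP section 12 says no departure from the protocol is planned.

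**The case against.** The strongest reply is that matched-only description is not settled. The descriptive sentence in protocol 9.7.1 names no set. Protocol 9.7, SAP 8.3 and SAP section 9 all point to all eligible patients. SAP 11.3 promises PACT-Q2 means before it turns to matching and does not confine them to matched patients. One can therefore read the plan as describing the FAS and matching only for the test. In addition, SAP section 5 and the SAP appendix refer table detail to mock-ups that are not part of the documents reviewed, and an unmatched table may exist there. This stands as far as it goes: the plan is ambiguous, and the count of 300 is conditional on the matched-only reading. It does not remove the problem, because the specific rule points to matched patients and only general rules point the other way.

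Restricting the comparison to matched patients is also legitimate, since the Cohort B primary outcome is a comparison between treatments. Nothing here argues against that.

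Three stronger readings should not be drawn:
- *The unmatched Pradaxa initiators are never described.* They are: baseline characteristics and PACT-Q1 cover all of Cohort B, and the safety analysis covers those with follow-up.
- *SAP 11.4 is the only other place that mentions PACT-Q2 means for Cohort B.* SAP 11.3 mentions PACT-Q2 means too.
- *Matching drops mainly older or higher-risk patients.* Protocol section 7 lists reimbursement criteria for Pradaxa but says nothing about the VKA case mix, and its list of conditions in which Pradaxa should not be considered would keep some high-risk patients off it. The direction is unknown. The 300 also follows from the 500:200 ratio alone and would arise if the two groups were identical.

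**Conclusion.** The concern holds in a conditional form. The specific text limits Cohort B PACT-Q2 analyses, and on its natural reading the Visit 2 and Visit 3 summaries, to matched pairs. That fits poorly with a descriptive objective and with the rules on all eligible patients and the FAS. Neither document specifies the summary by treatment that would resolve it.

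If the matched-only rule is applied at the planned split, at least 300 of 500 Pradaxa initiators (60%) have no PACT-Q2 result at Visits 2 and 3. The bound assumes that the estimated 500:200 split is realised, and it shrinks to nothing if the groups turn out equal. The caliper adds to it by an amount that depends on propensity separation the documents do not give. Missing questionnaires would reduce the numbers further under either reading. The gap concerns PACT-Q2 reporting only. It does not invalidate the matched comparison.

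**What to change.** In protocol 9.7.1 and SAP 11.3:

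1. State that PACT-Q2 at Visit 2 and at Visit 3 is summarised by treatment (Pradaxa, VKA) in all eligible Cohort B patients, that is, the FAS, with the number of completed questionnaires at each visit. Name this as the descriptive answer to Objective 1.
2. State that the matched pairs are used for the between-group comparison.
3. Show baseline characteristics of matched and unmatched initiators side by side, for both treatments, so that readers can see whom the comparison represents.

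At the planned sizes the descriptive tables would then cover up to 500 Pradaxa and 200 VKA initiators, against at most 200 and 200 in matched pairs. The sentence on PACT-Q2 means in SAP 11.4 should be given a visit, a population and a treatment split, or corrected if PACT-Q1 was meant. The mock-up tables should be aligned with the new text.

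The cost is one or two extra tables and a few lines of wording, from data already planned for collection.

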9.7.3 Safety analysis

Safety analyses will be performed separately for Cohort A and Cohort B, and will include all enrolled patients with an actual follow-up. Statistical analysis and reporting of AEs (i.e. Pradaxa® relevant ADR (serious and non-serious), fatal AEs, and pregnancies) will be descriptive in nature and based on BI standards. No hypothesis testing is planned. The assessment of safety will be based mainly on the frequency of adverse events, which includes

all serious adverse events. All adverse events will be summarized with the coding term, severity, and relationship to study drug by frequency tables with the counts and percentage.

In addition, occurrences of Pradaxa® relevant ADRs will be analyzed relative to the number of patients treated as well as observed person-years (i.e. time at risk). If no concurrent Pradaxa® treatment is administered, then events occurring within a washout period of 3 days after discontinuation of Pradaxa® treatment will be assigned to the last treatment given. This washout period will also be included as time at risk for derivation of total person-years. ADRs that deteriorate under treatment will also be considered as “treatment emergent”. Events occurring prior to first intake of Pradaxa® treatment prescribed at baseline, during periods without Pradaxa® treatment (excluding washout periods), or after the end of the 6-month follow-up (excluding washout periods) will not be considered treatment emergent events, and will not be included in the summary tables.

Furthermore, serious adverse events will be listed with event narration. Adverse events will be coded using the latest version of Medical dictionary for regulatory activities (MedDRA) terminology.

The following parameters will be included in the safety analyses:

- Adverse drug reactions
- Adverse drug reactions leading to discontinuation of anticoagulation treatment
- Serious adverse drug reactions
- Adverse events leading to deaths

9.7.4 Handling of missing data

Every reasonable attempt will be undertaken to ensure completeness of data collection. Imputation will be permitted, if deemed appropriate and on a case-by-case basis, depending on the extent and distribution of missing values, and will be described in the SAP.

The percentage of and reason for loss to follow-up will be summarized overall in Cohort A, by treatment in Cohort B, and by other relevant factors. In addition, if the proportion of patients with loss to follow-up is substantial enough (e.g. $\geq 10\%$) to warrant further investigation, baseline characteristics will be described for patients who are lost to follow-up in comparison to patients who have completed follow-up.

9.8 QUALITY CONTROL

Before the study launch, participating physicians will be trained on the protocol, safety reporting (as described in Section 11) and study conduct procedures by Boehringer Ingelheim (or designee).

In keeping with the non-interventional design employed in this study, site interaction (e.g., direct contact between site study staff or patients and representatives of the call center or the Study Coordinating Center) is minimized.

Twenty percent source data verification is planned in this study. At any time during the course of the study, the site study staff may contact designated personnel for clarification of study conduct. All information will be kept confidential.

During the study, the occurrence of any protocol violations will be determined. After these actions have been completed and the clinical database has been declared to be complete and accurate, it will be locked.

To ensure the data accuracy, completeness, and reliability, quality control will be the ongoing, concurrent review of data collection forms for completion and logic. The research staffs will preserve documented data from all sources on CRF, including lab test results, chart records, treatment conditions, physical examination, concomitant medication, and any safety information.

Boehringer Ingelheim or designated CRO will assure database quality processes are followed including the review of the data entered into the CRFs by investigational staffs for completeness and accuracy, and in accordance with the data validation plan.

9.9 LIMITATIONS OF THE RESEARCH METHODS

A non-interventional study is the most suitable design for obtaining information about the use of medicines in everyday therapeutic practice and thus for clarifying questions in everyday therapeutic practice. However, observational methodology inherits the limitation of selection bias and generalizability. In addition, the observational design intends to collect available data that are recorded on medical charts. The lack of data of interest may be one of the limitations.

A number of different types of bias that could influence the data collection and analysis from these cohorts are summarized below. Consecutive enrolment will be employed to minimize selection bias. The entry criteria are non-restrictive and will permit the enrolment of a broad patient population. The choice of treatment is at the discretion of the investigator. Missing data will be handled as appropriate (see Section 9.7.4) to lower the effect of missing values. All efforts will be made to minimize loss to follow-up in patients who are enrolled. Adjustment for covariates and propensity score matching (PSM) will be used to correct for identified confounders and channeling bias which could occur due to preferential prescribing in relation to different risks for events of interest (e.g. if Pradaxa® is prescribed more frequently to high risk patients than to other treatments, a high rate of outcome events could be expected in the Pradaxa® group). Patient reported outcomes will be assessed using validated questionnaires within a limited period of time to minimize recall bias which refers to the phenomenon when the outcomes of treatment (either good or bad) may colour the patient's recollection of events prior to or during the treatment.

